Encounter schedule. We expect the large majority of participants to prefer completing follow-up assessments via the Internet. We will develop a webpage and format questions so that they are easy to navigate and complete. Links to this questionnaire webpage will be e-mailed to participants at the time of the follow-up assessments. Paper questionnaires may also be mailed to study participants.

For our white, non-Hispanic population follow-up questionnaires will be sent as links to web-based surveys by e-mail and/or in hardcopy at 6 and 12 months after the prevention education session that denotes the origin of randomization, for our H/L population follow-up questionnaires will be sent as links to web-based surveys by e-mail and/or in hardcopy at 3 and 9 month after the prevention education session that denotes the origin of randomization. The follow-up assessments measuring skin self-examinations and sun protection behaviors will be identical to those given at baseline. The follow-up questionnaires also will assess cancer distress that may be attributed to receipt of explicit information about melanoma risk and/or *MC1R* genotype. Reminder communications will include a combination of telephone, email, text and mail.

Baseline and outcome measures. The baseline questionnaire administered via tablet (iPad) will be completed in the clinic in conjunction with the patient's visit, or will be filled out after the visit and returned via postal mail to the project team in a pre-paid envelope. In the baseline questionnaire the respondents are asked how they prefer to be contacted in future interactions either by e-mail or postal mail. All follow-up questionnaires and information will be available both as web-based and paper versions. See **Appendix** for baseline questionnaire.

Demographic variables. A number of demographic variables will be obtained such as age, gender, educational level. We also will inquire about additional background variables such as place of birth and family history of melanoma, other non-melanoma skin cancers, and other cancers.

Early detection and prevention measures. Information on sun exposure, skin examinations and sun protection behaviors will be collected using a published questionnaire with questions adapted to the specific needs of the proposal (Glanz et al. 2008). The self-reported sun exposure questions previously have been validated (Glanz et al. 2010).

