Follow-up assessments. To capture changes in early detection and prevention items over time, we will re-administer the 14-item measure for adults and 12-item measure for adults reporting for children at 6 and 12 months for our white, non-Hispanic population and at 3 and 9 month for our H/L population. A 12 month follow-up assures that all white, non-Hispanic participants are under observation for a full year, thus implicitly allowing all participants to experience both winter and summer months during which preventive behaviors may differ. We also will ask all participants to complete instruments assessing potential mediators at both follow-up times. The questionnaires used at follow-up will be e-mailed to participants as links to a web-based interface and/or mailed along with prepaid return envelopes.

Participant retention. To enhance retention at the 6 and 12 month time points for our white, non-Hispanic population and at 3 and 9 month for our H/L population, patients randomized to either the intervention or placebo arm will receive a series of two gift cards, each in the amount of \$20. The first will be mailed to participants along with the summary letter after the health education session. The second will be sent via U.S. mail after completion of the 12 month follow-up questionnaire for our white, non-Hispanic participants and after completion of the 9 month follow-up questionnaire for our H/L participants. Consented patients with low risk *MC1R* genotypes who are not selected for randomization will receive one \$10 gift card to be included in the mailing that conveys their ineligibility for further study participation.

We also will supplement monetary incentives for questionnaire completion with reminder post cards mailed the month preceding study assessments and birthday cards, which we have used in previous studies involving recruitment and retention of individuals at increased genetic risk for cancer in which telephone and in-person genetic counseling, disclosing test results, and periodic follow up assessments were undertaken for study participants (Pal et al. 2011, Christie et al. 2012, [name] et al. 2012). All communications will include postage paid response cards to update contact information. We conservatively estimate study attrition over the follow-up period at 20%.

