For Exploratory Aim 3, the 12-item measure for children age 10 years or younger as reported by the study participant (Section B) will be used. Study participants with at least one child 10 years of age or younger will complete Section B, and those participants with more than one child within this age range are instructed to answer questions in this section thinking about the oldest child. Section B elicits responses about sun protection behaviors of the child, including number of red or painful sunburns over the past year for white, non-Hispanics and over the past 9 months for our H/L populations.

Since intermittent sunburns in adolescence are strongly associated with future melanoma risk (Armstrong et al. 1993, Gandini et al. 2005), the outcome of particular interest for our exploratory aim is the number of red or painful sunburns that lasted a day or more over the past timeframe. This outcome is measured by Section B, Q5, with a range of possible responses of 0 through 5 times (5 indicating 5 or more red or painful burns). We will tailor the timeframe to correspond to the baseline, 6 or 12 month survey for white, non-Hispanic participants and at baseline, 3 or 9 months survey for H/L participants).

STATISTICS

There will be no merging of data between the white non-Hispanic study population and

the H/L study population data. We will conduct mutually exclusive analyses within each of these two study populations.

Non-Hispanic study population

For our white, non-Hispanic population, the number of participants, 500 with high risk *MC1R* genotypes required to participate in this study was based upon the power calculations below.

Study power, Aim 1. We determined that randomizing 500 participants with high risk *MC1R* variants (250 each to the intervention and placebo arm) ensures 80% power to detect mean differences in hours of sun exposure of 0.17, 0.50 and 0.84, respectively, when the estimated standard deviation of the observed means is equal to 1, 3 and 5, respectively, when comparing participants with high risk genotypes who are randomized to intervention to participants with high risk genotypes who are randomized to placebo. These calculations are based on two-sided, alpha=0.05 level tests assuming a conservative auto-correlation equal to 0.1 to account for the repeated measures of participants over time, and a conservative 20% study attrition.

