Aim 2. Hypothesis testing for the binary outcome of full-body examination (yes/no) will follow the general analytic outline used in Specific Aim 1. This outcome will be modeled using the logistic framework of the GEE approach (i.e. specifying a logit link function), which properly accounts for the induced correlation from the repeated measures on participants over time, to assess ITT differences. These ITT differences comparing the probability of skin examinations will be presented as odds ratios with corresponding 95% confidence intervals where models will include main effects for intervention (standard risk and prevention plus genetic education versus standard risk and prevention education only), time (0, 6, and 12 months), and interaction term between the intervention and time. The interaction term will be used to test for possible differences in effects over time in the two study arms as the main test of interest. In addition, the logistic GEE model will contain baseline covariates and variables related to study participation and/or attrition as appropriate.

Exploratory Aim 3. We will use the GEE Poisson or ordinal regression models as appropriate with main effects for the intervention, time, and interaction term between the intervention and time, and will adjust for date of study enrollment to account for seasonality. Specifically, we are interested in estimating the intervention's efficacy in reducing the average number of red or painful sunburns in children.

All statistical analyses will be conducted by a member of the Biostatistics Core under the direction supervision of [name].

Analyses among individuals with low-risk *MC1R* genotypes will be conducted in a similar fashion to those detailed above. Because we do not expect to see ITT differences in prevention behaviors comparing those who receive a risk and prevention education intervention that includes feedback of *MC1R* genotype to those who receive a risk and prevention education session that includes only standard information among the low-risk group, power analyses are omitted.

Pilot study Aim 1. The overall prevalence of *MC1R* genotypes will be calculated with corresponding 95% confidence intervals.

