All identifying data will be stored in secured and password protected files separate from all other research information, which will be identified by study identification number alone. The study database, into which information about participant contact and data from all surveys and genotype will be entered, will be hosted on secure computing servers developed by the Cancer Informatics Core and the Research Information Technology Department and will be restricted to only those individuals who are authorized to work on the study. Individual user accounts with passwords will be used to restrict access to the database. Specific privilege assignments within the database will also be employed to limit the types of functions that authorized users can perform to those functions that are appropriate for their role in the study.

RISKS

We believe there is minimal risk to study participants. There are no physical or medical risks or side effects associated with taking part in this study. Questionnaire instruments designed to assess skin protection behaviors do not include sensitive items, although some participants may feel a sense of responsibility while reporting the behaviors of their child under the age of 10 (for those participants with young children). There is no risk associated with giving a saliva sample. However, loss of confidentiality concerning risk and prevention behaviors or *MC1R* genotyping is always a risk to study participants, albeit we believe a negligible one.

There also may be emotional risk associated with feedback of genotype information including increased stress and worry, and in its most severe state suicide, although this would be unlikely. Emotional risk associated with feedback of genetic information also may manifest as feelings of stress and worry that one's child may develop melanoma. It is possible that stress and confusion may arise among persons with indeterminate or failed genetic tests, although we believe this scenario also is unlikely.

Participants in the study will be assured of strictest confidentiality. Special attention will be paid to the collection and storage of personal health information (name, address, phone number, etc.) to be used predominantly for tracking and follow-up purposes.

Of particular note, no identifying information will be collected relating to children of enrolled participants, and the study team will not attempt to identify said children under 18 years old.

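### Exploratory Aim 3 never fixes which child is followed, so as written a child who turns 11 during follow-up leaves the data or is replaced by a younger sibling (cheap improvement, minor)

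*Combined protocol and SAP*

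**What the plan says.** Under Primary Outcome of the Study, the text on Exploratory Aim 3 sets two rules. The first is who answers: "Study participants with at least one child 10 years of age or younger will complete Section B". The second is which child they answer about: "those participants with more than one child within this age range are instructed to answer questions in this section thinking about the oldest child". The outcome is a count of red or painful sunburns, capped at 5.

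The measure is repeated. Follow-up assessments (Research Procedures) states that "we will re-administer the 14-item measure for adults and 12-item measure for adults reporting for children at 6 and 12 months" in the white, non-Hispanic study, and at 3 and 9 months in the Hispanic/Latino (H/L) study. Encounter schedule adds: "The follow-up assessments measuring skin self-examinations and sun protection behaviors will be identical to those given at baseline". One adaptation of the child item is described, and it concerns the recall window: "We will tailor the timeframe to correspond to the baseline, 6 or 12 month survey for white, non-Hispanic participants", with a parallel statement for H/L participants.

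Risks states that "no identifying information will be collected relating to children of enrolled participants". The analysis, under Statistics, Exploratory Aim 3, reads: "We will use the GEE Poisson or ordinal regression models as appropriate with main effects for the intervention, time, and interaction term", adjusted for enrolment date. The power section gives no power for this aim because the proportion of participants with a young child is unknown.

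**The concern.** Both rules turn on the child's age, and nothing visible says that they are applied once, at baseline. A parent who follows them at each survey faces one of two situations when the reported child turns 11:

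- With no other child in range, the parent no longer qualifies for Section B, and the follow-up record is lost.
- With a younger child in range, the instruction now points to that sibling. The difference between surveys is then a difference between two children of different ages.

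Conversely, a participant whose first child is born after baseline could enter with no baseline value.

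The text describes no index-child marker, child's age or change-of-child item, so the analyst may be unable to tell these cases apart. The objective in Study Purpose and Hypothesis is fewer sunburns in participants' children at short and long term, so it matters which child each survey describes.

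**Working it through.** The plan gives no figure for Aim 3 to reproduce. The check asks how many reported children would age out and whether that would disturb the treatment contrast.

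**Elapsed time.** Surveys are timed from the education session (Encounter schedule), which takes place within 1-2 months of enrolment (Consent Process). Measured from baseline:

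- white, non-Hispanic: first survey at 7-8 months, last at 13-14 months
- H/L: first survey at 4-5 months, last at 10-11 months

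**One child in range.** Assume age uniform from 0 to under 11 years. The share turning 11 within m months is (m/12)/11.

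| Survey | m (months) | Share aged out |
|---|---|---|
| White, non-Hispanic, first | 7-8 | 5.3-6.1% |
| White, non-Hispanic, last | 13-14 | 9.8-10.6% |
| H/L, first | 4-5 | 3.0-3.8% |
| H/L, last | 10-11 | 7.6-8.3% |

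If ages were instead uniform from 5 to under 11, the divisor is 6 and the share at 13-14 months is 18.1-19.4%.

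**Older of two children in range.** With a sibling gap of g years, both children are in range only if the older is between g and 11. Assuming uniform age over that interval, the share is (m/12)/(11 - g). At 13-14 months:

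- g = 1.5: 1.083/9.5 to 1.167/9.5 = 11.4-12.3%
- g = 3: 1.083/8 to 1.167/8 = 13.5-14.6%
- g = 5: 1.083/6 to 1.167/6 = 18.1-19.4%

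Every gap here is at least 18 months, longer than the 14 months of follow-up. The younger child is therefore still in range when the older leaves it, and all of these cases are swaps rather than exits.

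**Mixed families.** A simulation assumed 1-3 children, gaps of 1.5-5 years and the oldest child's age uniform over 0-18. It covered two family-size mixes. At 12 months 12.8-13.8% had aged out: 5.9-7.6% switched to a sibling and 6.3-7.0% had no eligible child left. At 14 months the total was 15.0-16.2%.

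**Head count.** If 10-30% of the 500 high-risk white, non-Hispanic participants have an eligible child (assumption) and 9-18% of those children age out, the number affected runs from 500 x 0.10 x 0.09 = 4.5 to 500 x 0.30 x 0.18 = 27.

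**Effect on the arm-by-time contrast.** Let a fraction s of follow-up reports in each arm come from a sibling whose sunburn rate is r times the index child's. Let the intervention rate ratio be the same for both children. The follow-up mean in each arm is then multiplied by 1 - s(1 - r), and this factor cancels between arms. With 6% swapped and 5% dropped, s = 0.06/0.95 = 0.063. With r = 0.7 the factor is 1 - 0.063 x 0.3 = 0.98. A Poisson simulation with a true rate ratio of 0.80 agreed: the interaction ratio was 0.799 without swaps or drop-outs and 0.801 with them, while the control-arm time ratio moved from 1.00 to 0.98.

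**The case against.** The strongest reply is that re-selection of the child at each survey is an inference. The protocol says who completes Section B and about which child, but not that age is reassessed each time. The wording and routing sit in an appendix that is not in the text. This stands as a limit: if the questionnaire ties follow-up to the baseline child, a sentence in the protocol settles the matter. The statement that follow-up instruments are identical is also weaker evidence than it looks, since the recall window is tailored. Even so, no visible text fixes the child, and the rules as stated point to re-selection.

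A reader might infer four stronger things that the documents do not support:

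- **That the treatment contrast is biased or diluted.** Ageing out is unrelated to arm, and the check above found no shift when the effect is the same in siblings.
- **That the GEE is invalid.** The randomised unit is the parent. Robust inference clustered on the parent does not need the same child at each survey, and the stated target is the average number of sunburns in children.
- **That the privacy statement makes swaps undetectable.** It bars identifying information only. Age in completed years could be recorded, and Section B may already ask for it.
- **That about 19-20% of two-child families are affected.** That figure, 1 - (1 - share)^2, treats siblings' ages as independent. Fixed gaps give 11-19%.

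It is also fair that the aim is exploratory and unpowered, and that following a child past 10 collects answers outside the measure's stated age range.

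**Conclusion.** The gap is real and minor. As the text stands, the reported child is not fixed, and about 10-11% of single index children would pass out of range by the last white, non-Hispanic survey and about 8% by the last H/L survey. For the older of two children the white, non-Hispanic share is about 11-19%. These figures rest on assumed uniform ages and sibling gaps of 1.5 to 5 years; an older age mix would raise the single-child share. The cost is avoidable follow-up loss, added to the 20% attrition already expected, plus between-sibling noise and a time trend that does not describe one child. No primary outcome, sample size or primary analysis is touched. The change is worth making because a swap is hard to reconstruct afterwards and easy to prevent.

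**What to change.** 1. Define the index child at baseline as the oldest child aged 10 or younger at that time, and record age in completed years. This is non-identifying and compatible with the Risks section.
2. At both follow-ups, direct Section B to the same child the participant answered about at baseline, even if that child has since turned 11. The web system can pre-fill the baseline age as a prompt.
3. Record the child's current age at each follow-up as a check on identity.
4. Base the Aim 3 model on participants who had an index child at baseline.

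If the questionnaire already does this, state it in the protocol. By construction, age-driven swaps and exits then fall to zero. The cost is one reworded instruction and a short age field, with no added participants or visits. The downside is that a few reports will concern an 11-year-old, or rarely a child just turned 12 (just under 11 at baseline plus 13-14 months), slightly outside the measure's stated range.

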MC1R variants in Hispanic populations living in the Tampa Bay area. Melanoma incidence is trending upward among Hispanics living in the United States and Puerto Rico (Gonzalez-Fernandez and Sanchez, 1999; Hu et al. 2009). Of particular concern is the poorer overall survival from melanoma among Hispanics due to diagnoses at late stage disease (Hu et al. 2009; Rouhani et al. 2010; Jaimes et al. 2013). However, information on the prevalence and distribution of *MC1R* variants in Hispanic individuals is limited. Knowledge of the spectrum and distribution of the *MC1R* genotypes among Hispanic individuals will lay the foundation for future investigations of whether *MC1R* variants are robust markers of melanoma risk in this population, and by extension whether interventions based on inheritance of high-risk *MC1R* genotype—with the goal of increasing melanoma prevention behaviors—may be generalizable to Hispanic populations.

Using *MC1R* genotype to impact skin cancer risk behaviors in Hispanics/Latinos. The incidence of melanoma and/or keratinocyte (i.e., squamous cell and basal cell) skin cancers is trending upward among Hispanic/Latinos (H/L) living in Florida and Puerto

Rico (Gonzalez-Fernandez and Sanchez, 1999; De La Torre-Lugo et al. 2010; Hu et al. 2009). Feedback of genetic risk information has been suggested to motivate skin cancer prevention behaviors, and H/L are receptive to receiving this type information (Smit et al. 2016; Lynce et al. 2016). These activities may be important to H/L populations who have decreased awareness and risk perception of melanoma.

STUDY PURPOSE AND HYPOTHESIS

The primary objectives of this project are to:

- **Evaluate the impact of receipt of *MC1R* genotype on personal sun protection behaviors.** Determine the efficacy of a risk and prevention education session, which includes feedback of inherited *MC1R* genotype and corresponding information about genetic risk, to decrease sun exposure and increase sun protection behaviors at both short term (6 months) and long term (12 months) follow-up for our white, non-Hispanic population; for our H/L population, follow-up will occur at 3 and 9 months.

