Study power, Aim 2. We estimate a 20% incidence of having a skin examination with the past 9 months among control participants, with a range of 15% to 35%, and estimate study attrition of 20%. Using these estimates, we determined that randomizing 400 participants with high-risk *MC1R* variants (200 per study arm) ensures 80% power to detect an odds ratio of at least 1.95 to 1.73 when comparing participants with high-risk genotypes randomized to intervention versus those randomized to control for the skin examination (yes/no) outcome.

General approach. All analyses will be done within SAS, version 9 or later, primarily using PROC UNIVARIATE, FREQ and GENMOD. In the primary analyses, we will use an intention-to-treat (ITT) approach in which participants are analyzed in their randomized conditions regardless of the number of interventions or number of follow-up assessments they complete. Two-sided tests will be used for all hypotheses. We will assess the data for missing and out-of-range values with basic statistical procedures, including univariate statistics and graphs (histograms, box and whisker plots, scatter plots, and Q-Q plots). We will investigate data quality and integrity before any statistical modeling to ensure unbiased estimation.

The primary aim of this proposal is to test for significant ITT differences in the proportion of study subjects participating in skin prevention behaviors over the 12-month follow-up period by comparing those who receive a risk and prevention education intervention that includes feedback of *MC1R* genotype to those who receive a risk and prevention education session that includes only standard information. Our two primary outcomes of interests are (1) the average hours per week (weekdays and weekend) spent outside between 10am – 4pm; and (2) the completion of a full body skin examination for skin cancer (yes/no) by self, partner or clinician.

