Aim 1. We will use a linear GEE regression model with main effects for the intervention (standard risk and prevention plus genetic education versus standard risk and prevention education only), time, and the interaction terms between the intervention and time. The interaction term will be the main test of interest as it assesses average departure from the slope due to the intervention. We will include other covariates related to dropout or involving potential baseline imbalances between the intervention groups as appropriate, as well as month of completion of the questionnaires to account for seasonality.

We will perform analyses to test whether participants and eligible non-participants differ on basic demographic variables using cross-sectional logistic or linear regression models for binary or continuous factors, respectively. We will perform attrition analyses to determine whether participants and dropouts differ on key variables. We will include these factors in the above ITT model to see if they affect the results. A few randomly missing observations have only a slight impact on power and do not introduce bias. However, large numbers of non-randomly missing values can bias results.

We also will conduct mediator analyses to determine whether the effect of the intervention on prevention behaviors is explained by health beliefs or cancer distress. We will use a series of models to examine whether (a) the intervention is predictive of the mediator, (b) the mediator is predictive of prevention behaviors in a multivariable model controlling for the intervention, and (c) the addition of the mediator to a

multipredictor model for prevention behaviors attenuates the estimated coefficient for the intervention. To assess mediation effects, we will use the approaches by Imai et al., which are available through add-on packages to existing statistical software (such as R and STATA) (Imai et al. 2010, Imai et al. 2012). Similar to the method of Preacher and Hayes (Preacher et al. 2008), their methods employ bootstrapping to estimate mediating causal effects . These analyses will be used to estimate the direct effect of the intervention via pathways other than through the posited mediator, its indirect effect via the mediator, and the degree of mediation. This approach will allow us to quantify the effect of the intervention due to the potential mediator (if any), which can inform future interventions or prevention strategies.

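### The 80% power stated for Aim 1 is not the power of the arm-by-time test named as the main analysis: it is 71–75% if the printed figure is a per-visit slope and 24–28% if it is a 12-month difference

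*Combined protocol and SAP*

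**What the plan says.** All of this concerns the white, non-Hispanic trial. Under STATISTICS, Study power, Aim 1, randomising 250 high-risk participants to each arm "ensures 80% power to detect mean differences in hours of sun exposure of 0.17, 0.50 and 0.84, respectively". Each of these three values belongs to one of three assumed spreads, in hours: "the estimated standard deviation of the observed means is equal to 1, 3 and 5". The calculation is two-sided at 0.05, and its other inputs are given as "assuming a conservative auto-correlation equal to 0.1 to account for the repeated measures of participants over time, and a conservative 20% study attrition". The high-risk sample size of 500 is said to rest on these power calculations. Participant retention repeats the loss: "We conservatively estimate study attrition over the follow-up period at 20" per cent.

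Under STATISTICS, Aim 1, the model is a linear GEE with main effects for arm and time, plus their interaction. "The interaction term will be the main test of interest as it assesses average departure from the slope due to the intervention". The same paragraph also writes "time, and the interaction terms between the intervention and time", in the plural. The Aim 2 text, which follows the Aim 1 outline, gives the times as 0, 6 and 12 months. The General approach says that "participants are analyzed in their randomized conditions regardless of the number of interventions or number of follow-up assessments they complete". The primary objective is "to decrease sun exposure and increase sun protection behaviors at both short term (6 months) and long term (12 months) follow-up".

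**The concern.** The power section speaks of a mean difference, while the named test concerns a change in slope. These are different quantities with different standard errors. The plan does not say whether 0.17/0.50/0.84 h is a slope per visit, a difference at 12 months, or an average over visits.

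Hours in the sun is one of two primary outcomes, and the high-risk sample size is justified partly by this figure. If the named test has less power than stated, a null result could be wrongly read as evidence against an effect of 0.168 SD. If the figure is a slope, readers will take the effect the trial can detect to be half its real size at 12 months.

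**Working it through.** **Inputs.** From the plan: two-sided alpha 0.05, 250 randomised per arm, correlation ρ = 0.1, 20% attrition (250 × 0.8 = 200 completers per arm), visits at 0, 6 and 12 months. The printed effects in SD units are 0.17/1 = 0.170, 0.50/3 = 0.167 and 0.84/5 = 0.168; I use 0.168. Assumptions: the SD is that of one participant's value at one visit, and correlation is exchangeable, with AR(1) as a sensitivity case. The detectable effect at 80% power is 2.8016 × SE (1.960 + 0.8416).

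**Slope test.** With visits coded 0, 1, 2 and complete data, the estimated slope is (12-month value − baseline)/2. The arm difference in slope has SE = √((1 − ρ)/n) in SD units.

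**Where the printed values could come from.**
- *Slope, 250 complete per arm, no attrition.* SE = √(0.9/250) = 0.0600. The detectable slope is 2.8016 × 0.0600 = 0.168 SD, or 0.168/0.504/0.840 h. This matches all three printed values but leaves out the attrition.
- *Mean over all three visits, 200 completers plus 50 partial records per arm.* The detectable difference is 0.169 SD if all 50 leave after baseline, 0.166 if half leave after baseline and half after 6 months, and 0.163 if all leave after 6 months. This uses the stated inputs and comes close, but it is not the named test and it averages in a pre-intervention visit. If the effect exists only at 6 and 12 months, this test has about 39–47% power at 0.168 SD.
- *SD taken as that of each participant's mean.* 2.8016 × √(2/n) gives 0.25 (n = 250) to 0.28 (n = 200), so this does not explain the figures.

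**Named test, 0.168 SD read as a per-visit slope, attrition applied.**
- 200 completers: SE = √(0.9/200) = 0.0671; 0.168/0.0671 = 2.504; power = Φ(2.504 − 1.960) = 70.7%.
- Dropouts' earlier visits kept (GLS): SE ≈ 0.0638–0.0639; power 74.8–75.0% over the three dropout timings.
- AR(1): 66.6% (completers), 71.2–71.3% (partial data).
- The implied 12-month difference is 2 × 0.168 = 0.336 SD, or 0.34/1.01/1.68 h.

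**Named test, 0.168 SD read as the 12-month difference, linear time.** The slope is 0.168/2 = 0.084.
- 200 completers: 0.084/0.0671 = 1.252; power = Φ(1.252 − 1.960) ≈ 24.0%.
- With complete data the 6-month visit has no weight, so an equal effect (0, d, d) and a growing one (0, d/2, d) both give 24.0%.
- Partial data kept: 26.0–26.1% (growing) and 27.3–27.9% (equal).
- AR(1), 200 completers: 22.3%.

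**Other time codings, equal effect at both follow-ups, 200 completers.** A 2-df categorical interaction gives 23.4% (exchangeable) or 22.2% (AR(1)). The average of the two interaction terms gives 30.4% or 28.8%. Across these tests, both structures and all dropout timings, partial data give 25–35%. With no attrition the maximum is 37%.

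**Simulation check.** GEE with exchangeable working correlation and robust SE, 4000 runs:

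| Effect at 0, 6, 12 months | 200 completers | half-and-half partial data |
|---|---|---|
| 0, d, 2d (slope) | 70.7% | 75.1% |
| 0, d, d | 24.9% | 27.9% |
| 0, d/2, d | 23.8% | 25.7% |
| none | 5.9% | 5.1% |

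**Dependence on ρ** (values other than 0.1 are assumptions; exchangeable). The slope reading reaches 80% at ρ = 0.28 with 200 completers, or 0.21–0.22 with partial data, and 92% at 0.5 with completers. The linear test of an equal difference has 39% at 0.5, 58% at 0.7, and reaches 80% only near 0.82 (200 completers).

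**The case against.** The best defence is that the printed values are per-visit slopes. That reading fits all three to the printed precision, it suits a main test described as a departure from slope, and it explains why 0.1 is called conservative, since low correlation inflates the variance of a slope. On this view the power section and the test do agree, the only slip is the missing attrition, and the shortfall is 5 to 9 points. It would disappear at a correlation of 0.2 to 0.3, and covariates could help further. Nothing in the plan says that 0.17/0.50/0.84 h is a 12-month contrast.

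Much of this stands. The slope reading is the best numerical fit, and the 24–28% figure depends on a reading the plan does not state. Because the plan keeps participants with incomplete follow-up, 75% is more relevant than 71%. But the plan says that 20% attrition is included and that 250 per arm are randomised, so 250 cannot mean completers, and the claim must hold at the plan's own correlation. The power text does not count covariates. The slope reading also leaves the effect misdescribed, because what is called a mean difference would be half the difference between arms at 12 months.

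Dropping the arm main effect, so that the arms share a baseline mean, would raise the slope reading to about 95–96%, but would give only about 44–47% for a 12-month difference of the printed size that builds up linearly. The plan's model includes that main effect.

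**Conclusion.** The concern holds. At correlation 0.1 and 20% attrition, the interaction test in the planned model does not have 80% power for 0.168 SD on any reading examined. The shortfall is modest, at 71–75% (67–71% under AR(1)), if the figure is a per-visit slope. It is large, at 24–28%, if the figure is a 12-month difference under linear time with exchangeable correlation. The documents do not settle which reading was intended, nor the time coding, the correlation structure or the way attrition enters. The results rest on the plan's correlation of 0.1, and a higher true correlation would improve them. This must be corrected, because a primary outcome and the sample-size justification depend on it.

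**What to change.** State in the Aim 1 power section whether the mean difference is a per-visit slope or a difference over follow-up. Give the time coding, the correlation structure and how attrition enters. Then restate the detectable value for the test used. With 200 completers per arm and ρ = 0.1 (exchangeable):

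- per-visit slope: 2.8016 × 0.0671 = 0.188 SD, or 0.19/0.56/0.94 h, printed with the 12-month difference it implies;
- 12-month difference tested by the linear interaction: 2 × 0.188 = 0.376 SD, or 0.38/1.13/1.88 h.

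Keeping 0.168 SD per visit at 80% power would instead need about 251 completers, or 251/0.8 ≈ 314 randomised per arm.

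An optional alternative suits an objective framed at both follow-ups: make the main test the arm effect averaged over 6 and 12 months, with baseline hours as a covariate. Its SE is √(2 × (0.55 − 0.01)/200) = 0.0735, where 0.55 = (1 + ρ)/2 and 0.01 = ρ². The detectable difference is 0.206 SD, or 0.21/0.62/1.03 h. At 0.168 SD this test has about 63% power, and 80% would need about 300 completers per arm, so the stated figure must still be revised. This switch is a design choice and is not needed to correct the inconsistency.

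The cost is SAP wording and a less favourable stated difference. Baseline hours and both follow-ups are already collected.
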